## 5.4.4 Other Efficacy Analyses

The associations between the presence of FDA-defined valvulopathy and Change from Baseline in body weight or BMI, at 1 year, will be analyzed using logistic regression including stratification variable (presence of established CV disease or CV risk factors without established CV disease), baseline weight (or BMI), age, and Week 52 weight change (or BMI change) as independent variables in the model. The model will be run for each treatment group separately and for all patients (with their treatment group not included in the model). The odds ratio, p-value and 2-sided 95% CI will be calculated, along with the regression coefficients, standard errors and 95%CIs. The ITT analysis set in subjects with FDA-defined Valvulopathy at Baseline will be used for this analysis.

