Pharmacotherapy can play a significant role in weight management programs and is often combined with behavioral changes to enhance weight loss beyond that which is normally achieved with diet and exercise alone. Current pharmacotherapies offer the potential to significantly augment weight loss when combined with diet and exercise. The beneficial effects of many available agents are in part offset by side effects that can include increased BP (agents with sympathomimetic activity) or unpleasant gastrointestinal events (orlistat).

Over the past 2 decades there have been numerous attempts to develop safe and effective drugs for weight management. However, most have failed to gain approval or have been withdrawn from the market due to serious safety concerns. Furthermore, no agent has demonstrated long-term cardiovascular (CV) benefit.

APD356/BELVIQ[®] (lorcaserin hydrochloride) is a selective serotonin 2c receptor agonist which was approved by the US Food and Drug Administration (FDA) on 27 June 2012 as an adjunct to a reduced-calorie diet and increased physical activity for chronic weight management in adult patients with a BMI greater than or equal to 30 kg/m² (obese), or adult patients with a BMI

greater than or equal to 27 kg/m² (overweight) in the presence of at least 1 weight-related comorbid condition.

The Phase 3 clinical evaluation of lorcaserin HCl in clinical trials of more than 7700 patients, including 604 patients with T2DM, demonstrated clinically meaningful efficacy and a safety profile that includes minimal and easily managed risks. In each of the individual studies and in the pooled efficacy analyses, the lorcaserin HCl 10 mg twice daily (BID) dose met prespecified primary endpoints for weight loss:

- A significantly greater proportion of patients taking lorcaserin HCl lost $\geq 5\%$ of baseline body weight at 1 year as compared to placebo
- The mean weight loss at 1 year in patients taking lorcaserin HCl was significantly greater than that in patients taking placebo
- A significantly greater proportion of patients taking lorcaserin HCl lost $\geq 10\%$ of baseline body weight at 1 year as compared to placebo
- The weight loss efficacy was supported in each trial by favorable trends in multiple other measures of CV risk, glycemic control and quality of life.
- Glycosylated hemoglobin (HbA_{1c}) was statistically significantly reduced by 0.5% among patients with T2DM compared to placebo.

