## 3.3 OVERALL STUDY DESIGN AND PLAN

This will be a multicenter, randomized, double-blind, placebo-controlled, parallel-group study in overweight and obese subjects with CV disease and/or multiple CV risk factors. Approximately 12,000 subjects will be randomized to 2 treatment groups in a ratio of 1:1, stratified by the presence of established CV disease (~80%) or CV risk factors without established CV disease

(~20%). The 80% of subjects in the established CV disease strata will consist of a group with T2DM (approximately 30% of the total number of subjects in the study) and a group without T2DM (approximately 50% of the total number of subjects in the study). The 20% of subjects in the strata with CV risk factors but without established CV disease will all have T2DM, as well as additional risk factors. Therefore, approximately 50% of the total number of subjects in the study will have T2DM (Table 1).

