- Change from Baseline in HbA1c at 6 months in subjects with T2DM at Baseline will be analyzed using an analysis of covariance (ANCOVA) model with treatment and stratification variable (presence of established CV disease or CV risk factors without established CV disease) as factors, and baseline HbA1c, as a covariate. Comparison between lorcaserin HCl and placebo will be made at 6 months. The estimated treatment difference between lorcaserin HCl and placebo and the 2-sided 95% CI will be calculated. The T2DM Analysis Set will be used for this analysis. (revised per Amendment 01)

In addition to the analysis of the ECHO data from this study, the following analyses will be repeated by pooling the ECHO data from this study with the data from the 3 pivotal lorcaserin

HCl studies (APD356-009, -010, and -011) with terms added for study and treatment by study interaction term in the model in order to account for the variability of the different studies.

- The proportion of subjects who meet FDA-defined valvulopathy in echocardiographically determined heart valve changes will be analyzed using logistic regression including treatment as a factor and baseline BMI as a covariate. Comparison between lorcaserin HCl and placebo will be made at 1 year. The FDA-defined Valvulopathy Analysis Set will be used for this analysis.
- The proportion of subjects with FDA-defined valvulopathy at Baseline who demonstrate worsened FDA-defined valvulopathy will be analyzed using logistic regression including treatment as a factor and baseline BMI as a covariate. A comparison between lorcaserin HCl and placebo will be made at 1 year. The ITT analysis set in subjects with FDA-defined valvulopathy at Baseline will be used for this analysis. (revised per Amendment 01)
- The change from Baseline in echocardiographically-determined pulmonary arterial systolic pressure will be analyzed using a mixed-effects model with repeated measures with treatment as a factor and baseline BMI as a covariate. Comparison between lorcaserin HCl and placebo will be made at 1 year and the corresponding 2-sided 95% CI will be calculated. (revised per Amendment 01) The ITT will be used for this analysis.

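### The all-patient model of weight change and valvulopathy in SAP 5.4.4 omits treatment, so its weight odds ratio would be modestly confounded by arm if lorcaserin affects valves

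*SAP*

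**What the plan says.** SAP 5.4.4 (Other Efficacy Analyses) examines "The associations between the presence of FDA-defined valvulopathy and Change from Baseline in body weight or BMI, at 1 year". The model is a logistic regression with the CV stratification variable and "baseline weight (or BMI), age, and Week 52 weight change (or BMI change) as independent variables in the model". Three fits are specified in one sentence: "The model will be run for each treatment group separately and for all patients (with their treatment group not included in the model". The SAP does not say which of the three governs interpretation. On output it says "The odds ratio, p-value and 2-sided 95% CI will be calculated", and on population "The ITT analysis set in subjects with FDA-defined Valvulopathy at Baseline will be used for this analysis".

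Two other places bear on the point:

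- **Effect on weight.** Protocol section 7 says of the Phase 3 programme: "The mean weight loss at 1 year in patients taking lorcaserin HCl was significantly greater than that in patients taking placebo".
- **Effect on valves.** SAP 5.4.3 compares the arms on new and on worsened valvulopathy at 1 year. Each outcome "will be analyzed using logistic regression including treatment as a factor and baseline BMI as a covariate". The worsening analysis uses the same baseline-valvulopathy subset as 5.4.4.

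The SAP gives no reason for leaving treatment out. Its revision history says only that the analysis was added after discussions with the study group and the sponsor's clinical team.

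**The concern.** Treatment shifts the predictor, weight change. The plan itself treats a drug effect on the valves as an open question, because 5.4.3 tests for one in these same subjects. A variable that may influence both predictor and outcome is a potential confounder, and the all-patient fit leaves it out. If the drug raises the odds of valvulopathy by a route other than weight, lorcaserin subjects will have both more weight loss and more valvulopathy. The pooled fit will then show an association between the two even if none exists within either arm. A true protective association could be masked in the same way.

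What is at stake is the reading of one supportive odds ratio, with its p-value and interval. Of the three fits it rests on the largest sample, so it is easily the one that gets quoted.

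**Working it through.** The documents give no sample size, effect size or power for this analysis, so there is no figure of the plan's to reproduce. The check asks how large a weight association appears when the true one is zero.

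**Inputs**

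- Allocation is 1:1 (SAP 3.3: "Approximately 12,000 subjects will be randomized to 2 treatment groups in a ratio of 1:1"), assumed to hold roughly in the subset. The arm indicator then has variance 0.5 × 0.5 = 0.25.
- Lorcaserin increases weight loss (Protocol section 7), but the documents give neither the difference nor the SD. Assumed: arm difference D = 2.5 to 4 kg and within-arm SD s = 5 to 7 kg.
- Drug odds ratio on valve status: assumed 1.5, 2.0 or 3.0.
- Size of the subset: not given; 180 to 360 assumed. The whole echocardiography substudy is about 3600 (Protocol synopsis, Study Design).

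**Closed form.** To first order, the omitted-variable bias in the weight coefficient is ln(OR) times the slope of the arm indicator on weight loss. Per 5 kg lost:

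spurious log OR = 5 × ln(OR) × 0.25D / (s² + 0.25D²)

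- Low end (D = 2.5, s = 7): 5 × 0.625 / (49 + 1.5625) = 0.0618
- High end (D = 4, s = 5): 5 × 1 / (25 + 4) = 0.1724

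| Drug OR | Low end | High end |
|---|---|---|
| 1.5 (ln = 0.4055) | exp(0.0251) = 1.03 | exp(0.0699) = 1.07 |
| 2.0 (ln = 0.6931) | exp(0.0428) = 1.04 | exp(0.1195) = 1.13 |
| 3.0 (ln = 1.0986) | exp(0.0679) = 1.07 | exp(0.1894) = 1.21 |

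**Check by simulation.** Weight loss was put in SD units, with arm difference d = D/s of 0.2 to 0.6, placebo-arm outcome probability 0.05 or 0.70, and one million subjects per setting. For d = 0.4 and drug OR 2.0 the pooled odds ratio per SD was 1.064 to 1.065 (closed form 1.069). For d = 0.6 and OR 3.0 it was 1.154 to 1.156 (closed form 1.163). So the closed form runs slightly high. The strongest corner in the table has d = 4/5 = 0.8, which is outside the simulated grid and rests on the formula alone.

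With no drug effect the pooled odds ratio was 0.99 to 1.01. With treatment added, the weight odds ratio was 0.99 to 1.01 throughout. Little of the drug effect moves to the weight term: at d = 0.4 and OR 2.0, ln(1.064)/ln(2.0) = 0.062/0.693, or about 9% per SD.

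**False-positive rate of the weight term** (two-sided 0.05, 1000 replicates; without treatment / with treatment):

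| d, drug OR | N = 180, outcome 0.70 | N = 360, outcome 0.05 | N = 360, outcome 0.70 |
|---|---|---|---|
| 0.4, 1.5 | 6.4% / 5.5% | 6.4% / 5.9% | 7.4% / 5.8% |
| 0.4, 2.0 | 6.3% / 4.3% | 6.4% / 5.1% | 7.7% / 4.5% |
| 0.6, 2.0 | 7.1% / 5.0% | 7.7% / 5.9% | 12.6% / 6.2% |
| 0.6, 3.0 | 12.6% / 4.6% | 10.8% / 4.3% | 19.7% / 5.1% |

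The simulation standard error near 5% is √(0.05 × 0.95 / 1000) = 0.7 percentage points, so several of the smaller excesses are barely distinguishable from noise. A further run with 300 subjects, a 30% outcome and s = 6 kg gave 5% at drug OR 1.5, 11% at OR 2.0, and 16% at OR 2.0 with a 4 kg difference.

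**The case against.** The strongest reply is that the safeguard sits in the same sentence. Treatment is constant within each arm, so the by-arm fits cannot be confounded by it. That each uses about half the data is a weak complaint, because the two estimates can be combined from the coefficients and standard errors that 5.4.4 already asks for. Any divergence of the pooled result would also be visible beside them. This stands. It leaves only that the SAP neither specifies that combination nor says which fit to interpret.

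A reader might infer that the plan means to attribute a drug effect on valves to weight loss, and so explain a valve signal away. The documents do not support this. SAP 5.4.4 speaks of associations and nowhere says the all-patient odds ratio will be read causally. The arms are compared on valve outcomes in 5.4.3, for this study and pooled with three pivotal studies, and in 5.8 from 2 years onward. Those models include treatment, and nothing in 5.4.4 alters their estimates. They do not, however, correct the 5.4.4 weight coefficient.

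A reader might also infer large error rates by taking the sample to be close to the whole echocardiography substudy. With N = 3000 the simulated rates run from 7% to 93%. But 5.4.4 is restricted to subjects who already have valvulopathy at Baseline, so those figures do not apply. Presence at 1 year in that set is largely persistence, for which a 5% outcome is also implausible. Whether that set is the right one is a separate question.

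**Conclusion.** The point holds as a minor one. The all-patient fit omits a variable known to affect the predictor, and 5.4.3 allows that it may affect the outcome in the same subjects. If it does, other than through weight, the all-patient weight odds ratio is confounded by arm. For a harmful drug effect, the bias makes weight loss look associated with valvulopathy.

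The size is modest: about 1.03 to 1.07 per 5 kg lost for a drug odds ratio of 1.5, and 1.04 to 1.13 for 2.0. With a few hundred subjects the false-positive rate is roughly 5% to 20%, and the top of that range needs a drug odds ratio of 3.0. These figures rest on an assumed arm difference, SD, drug effect and subset size, none of which is in the documents. With no drug effect on valves there is no bias from this source. The analysis is supportive and outside the testing hierarchy in SAP 5.3.3, so no primary or key secondary conclusion depends on it.

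**What to change.** In SAP 5.4.4, replace the parenthetical that excludes treatment from the all-patient run with wording that puts treatment in as a factor. Optionally add a treatment-by-weight-change term to test whether the two arm slopes differ. Keep the by-arm fits. If the unadjusted all-patient fit is retained, label it descriptive and state that interpretation rests on the adjusted or within-arm results.

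The cost is one phrase and one model term, with no new data. The adjustment removes confounding by arm only. Week 52 weight change is measured after randomization and may share other causes with valve status, so the weight coefficient remains an association.

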9.7.1.2 Definitions of Analysis Sets

The Safety Analysis Set will be the group of subjects who received at least 1 dose of study drug and had at least 1 postdose safety assessment.

The Intent-to-Treat set (ITT) will be the group of all randomized subjects regardless of whether they took study drug or not.

- Total Time Analysis Set: Using the ITT, events are counted that occur while subjects are on and off treatment. Subjects with no events who discontinue early or complete the study will be censored at their last study contact (see details in the SAP). This will be used for the primary analysis.
- On-Treatment plus 30 Days Analysis Set: Using the ITT, events are counted that occur while subjects are on treatment and up to 30 days from their last dose. Subjects with no events who discontinue early or complete the study will be censored at their last dose day plus 30 days.
- On-Treatment Analysis Set: Using the ITT, events are counted that occur while subjects are on treatment. Subjects with no events who discontinue early or complete the study will be censored at their last dose day.
- Prediabetes Analysis Set: This set includes all subjects in the ITT set without a history of any type of diabetes and who are prediabetic at Baseline. Definition of prediabetes will be found in the SAP. (revised per Amendment 01)
- Nondiabetes Analysis Set: This set includes all subjects in the ITT set without a history of any type of diabetes at Baseline. Definition of nondiabetes will be found in the SAP. (revised per Amendment 01)

T2DM Analysis Set: This set will be all subjects in the ITT who have T2DM at Baseline.

FDA-defined Valvulopathy Analysis Set: This set will be all subjects in the ITT without FDA-defined valvulopathy at Baseline. The data from this study will be pooled with the data from the 3 pivotal lorcaserin HCl studies (APD356-009, -010, and -011).

The PD Analysis Set will be the group of subjects who have both baseline and at least 1 postbaseline assessment of at least 1 PD parameter.

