# Secondary Endpoints Assessing Cardiac Valve Function and Pulmonary Arterial Pressure: (revised per Amendment 02)

- Proportion of subjects without FDA-defined valvulopathy at Baseline who develop FDA-defined valvulopathy at 1 year (see Section 8.4 for definition)
- Proportion of subjects with FDA-defined valvulopathy confirmed by documented objective assessments at Baseline who demonstrate worsened FDA-defined valvulopathy (see Section 8.4.1 for definition) at 1 year (revised per Amendment 01).
- Change from Baseline in estimated pulmonary artery systolic pressure at 1 year

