## 5.2 STUDY SUBJECTS

#### **5.2.1** Definitions of Analysis Sets

The number (percent) of subjects included in each analysis set will be presented by analysis set, treatment group and overall. The description of the analysis data sets are:

- The Safety Analysis Set: will be the group of subjects who received at least one dose of study drug and had at least one post dose safety assessment.
- The Intent-to-Treat (ITT) Set: will be the group of all randomized subjects regardless of whether they took study drug or not. This is the same as the Full Analysis Set.
- Total Time Analysis Set: Using the ITT, events are counted that occur while subjects are on and off treatment. Subjects with no events will be censored at their last study contact or at the visit following Sponsor Notification of Study Completion, whichever

- occurs first. This analysis set will be used for the primary analysis. See Section 8.5 for censoring algorithm.
- On-Treatment plus 30 Days Analysis Set: Using the ITT, events are counted that occur
  while subjects are "on treatment" and up to 30 days from their last dose. Subjects with
  no events who discontinue early or complete the study will be censored at their last dose
  date plus 30 days. See Section 8 for definition of "on treatment" and Section 8.5 for
  censoring algorithm.
- On-Treatment Analysis Set: Using the ITT, events are counted that occur while subjects are "on treatment". Subjects with no events who discontinue early or complete the study will be censored at their last dose date. See Section 8 for definition of "on treatment" and Section 8.5 for censoring algorithm.
- Prediabetes Analysis Set: This set includes all subjects in the ITT set without a history of any type of diabetes and who are prediabetic at Baseline (defined in Section 8).
- Nondiabetes Analysis Set: This set includes all subjects in the ITT set without a history of any type of diabetes at Baseline (defined in Section 8).
- T2DM Analysis Set: This set will be all subjects in the ITT who have T2DM at Baseline (defined in Section 8).
- FDA-defined Valvulopathy Analysis Set: This set will be all subjects in the ITT without FDA- defined valvulopathy at Baseline (defined in Section 8.4). The data from the ECHO sub-study will be pooled with the ECHO data from the 3 pivotal lorcaserin HCl studies (APD356-009, APD356-010, and APD356-011).

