#### 8.4 FDA DEFINED VALVULOPATHY AND PULMONARY ARTERIAL PRESSURE

The aortic and mitral valve regurgitation will be categorized as absent, trace, mild, moderate or severe. FDA-defined valvulopathy, or simply "FDA valvulopathy," stipulate that significant valvular regurgitation comprises **mild or greater aortic valve regurgitation and/or moderate or greater mitral valve regurgitation**. The ECHO sub-study data presents the mitral and aortic valve severity as 5 categories; ABSENT, TRACE, MILD, MODERATE, and SEVERE.

For each subject and visit a dichotomous variable will be created, where;

1 = mild or greater aortic valve regurgitation and/or moderate or greater mitral valve regurgitation

0 = aortic valve regurgitation is absent or trace and mitral valve regurgitation is mild or less.

For the secondary endpoints assessing cardiac valve function and pulmonary arterial pressure listed in Section 5.1.2 the ECHO sub-study data from this study will be pooled with studies ADP356-009, -010, and -011.

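### SAP 5.4.4 relates weight change to the presence of FDA-defined valvulopathy only in subjects who already have it at Baseline, a pairing that fits neither new onset nor worsening

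*SAP*

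**What the plan says.** SAP 5.4.4 (Other Efficacy Analyses) states: "The associations between the presence of FDA-defined valvulopathy and Change from Baseline in body weight or BMI, at 1 year, will be analyzed using logistic". The model is thus a logistic one. The covariates are the CV stratification variable, baseline weight or BMI, age, and the Week 52 change in weight or BMI. Odds ratios, p-values and 95% confidence intervals are to be reported. On the arms, it says: "The model will be run for each treatment group separately and for all patients (with their treatment group not included in the model". The population is given last: "The ITT analysis set in subjects with FDA-defined Valvulopathy at Baseline will be used for this analysis".

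Four other places bear on this:

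- **Coding, SAP 8.4.** "For each subject and visit a dichotomous variable will be created, where" 1 means aortic regurgitation of at least mild grade, mitral regurgitation of at least moderate grade, or both. 0 means that both valves are below those grades.
- **New onset, SAP 5.1.3.** The endpoint is: "Proportion of subjects without FDA-defined valvulopathy at Baseline who develop FDA-defined valvulopathy at 1 year".
- **Worsening, SAP 8.4.1.** This is any increase in aortic or mitral regurgitation from Baseline, in subjects with valvulopathy at Baseline.
- **Named set, SAP 5.2.1 and Protocol 9.7.1.2.** The FDA-defined Valvulopathy Analysis Set is, despite its name, the group without the condition: "This set will be all subjects in the ITT without FDA- defined valvulopathy at Baseline". Its definition also pools this study's echo data with the three pivotal lorcaserin studies.

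SAP 5.4.3 uses that named set for its 1-year comparison of lorcaserin with placebo: "The proportion of subjects who meet FDA-defined valvulopathy in echocardiographically determined heart valve changes will be analyzed using logistic regression". It uses ITT subjects with valvulopathy at Baseline only for the worsening comparison.

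**The concern.** An outcome worded as presence of valvulopathy, modelled on weight change over the first year, will be read as showing how weight change relates to valve findings. In subjects selected because they already have valvulopathy, it cannot show that. Every subject who could develop the condition is excluded, and progression in those who have it is not what the 1/0 code records.

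At stake is the interpretation of one supportive table. It would carry odds ratios, p-values and confidence intervals for each arm and for both arms combined, and they would describe something different from either valvulopathy endpoint defined elsewhere in the SAP.

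**Working it through.** The plan states no sample size, power or event count for this analysis, so there is no figure to reproduce. The check crosses the population in 5.4.4 with the coding in 8.4 and the endpoint definitions in 5.1.3 and 8.4.1.

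**Step 1: does anything in 5.4.4 lift the restriction?** No. The reference to all patients concerns pooling the two arms with treatment left out of the model. No other section gives a second population for this analysis.

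**Step 2: what can the outcome be in this set?** Every subject has code 1 at Baseline.

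| Reading of presence | Possible codes | What the model estimates |
|---|---|---|
| At Baseline | 1 only | Nothing; a logistic model cannot be fitted to a constant outcome |
| At 1 year | 1 or 0 | Persistence (1) against resolution to below the threshold (0) |

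The text does not settle the reading. The 1-year time point directly follows the weight or BMI change, and no separate time is stated for presence.

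**Step 3: new onset.** This needs code 0 at Baseline and code 1 at 1 year. Subjects in the set with code 0 at Baseline: 0. So possible new-onset cases: 0, at any prevalence.

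**Step 4: worsening.** Take a subject with mild aortic regurgitation at Baseline (code 1) and moderate at 1 year. Section 8.4.1 counts this as worsened. The code is still 1, the same as for a subject whose grade did not change. The code therefore does not separate worsening from stability.

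**Step 5: set sizes, as an illustration only.** Protocol 9.5.1.5 gives about 3,600 echo subjects. Baseline prevalence p is not in the documents and is assumed here.

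- With valvulopathy = 3,600 × p
- Without valvulopathy = 3,600 − 3,600 × p

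| Assumed p | In the set as written | Left out, at risk of new onset |
|---|---|---|
| 2% | 72 | 3,528 |
| 5% | 180 | 3,420 |
| 10% | 360 | 3,240 |

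The per-arm models would have about half the middle column each (1:1 randomization): 36, 90 or 180. All counts are before losses from missing 1-year echocardiograms or Week 52 weights.

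**Step 6: comparison of population lines.** The sentence in 5.4.4 matches, apart from one capital letter, the population sentence of the worsening analysis in 5.4.3. There it fits, because worsening is defined only in subjects who have valvulopathy at Baseline.

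**The case against.** The best defence is that the SAP says presence, not development. Whether existing valvulopathy is still present at 1 year, in relation to weight change, is a definable question, and a sponsor could want it answered. The SAP states no purpose for the analysis; its revision history attributes the addition only to discussions with the academic study group and the sponsor's clinical team. The analysis is also absent from the endpoint list and carries no alpha or decision rule. Because weight change arises after randomization and the model is run within arm or without treatment, it would be descriptive in any population.

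Much of this stands. A reader might infer that the SAP set out to estimate new onset and failed; no section states that aim. A reader might infer that the outcome will be almost always 1; the documents give no persistence rate or reader-variability figure, and a one-grade fall across the threshold turns a 1 into a 0. A reader might conclude that the population line was copied by mistake from 5.4.3; the near-identical wording makes that plausible but does not prove it.

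The defence does not rescue the text. Even a deliberate analysis of persistence would need its outcome and time point stated, and at present one of the two readings cannot be fitted at all.

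**Conclusion.** The point holds as a mismatch between population and outcome. As written, 5.4.4 can at most contrast persistence with resolution. It cannot estimate an association with new valvulopathy, because no subject in the set is at risk, and its code does not register worsening. These conclusions follow from the SAP's own definitions and need no assumption about prevalence. The set sizes do need one, and are illustrative.

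The reach is limited. A reader might infer that the valve-safety conclusions are compromised, but the documents do not support that. The 1-year treatment comparison for new valvulopathy (5.4.3) and those at 2 years and yearly thereafter (5.8) use the set without valvulopathy at Baseline, and worsening has its own analysis in the right population (5.4.3). The primary and key secondary tests do not depend on 5.4.4. It should be corrected because the correction is easy and the output would otherwise invite misreading.

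**What to change.** In SAP 5.4.4:

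1. Change the population to this study's echo subjects without FDA-defined valvulopathy at Baseline, that is, the FDA-defined Valvulopathy Analysis Set without the pooled data from the three pivotal studies.
2. State the outcome as new FDA-defined valvulopathy at 1 year.
3. If subjects with valvulopathy at Baseline are also of interest, keep them as a separate analysis with worsened valvulopathy, as defined in 8.4.1, at 1 year as the outcome.

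The cost is a small edit to the population, outcome and time-point wording. The echocardiograms and weights are already scheduled, so no new data are needed. The edit should be made before unblinding for the final analysis, so that the population is not chosen after results are seen.
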